4.4 Sample size calculation

It is expected that long-term taste and smell dysfunction are prevalent in 25% of the patients. As described in the introduction, taste changes were found in 24% of patients using immunotherapy(9). In this study, however, it is not reported whether these changes were reported spontaneously or were actively asked. It is therefore possible that the percentage of 24% will be even higher. From earlier studies in patients years after treatment of testis carcinoma or childhood cancer, it is know that about 25% of these (former) patients have long-term taste and smell changes(21,22). Based on this information, the percentage of 25% was determined.

As caregivers with a history of disorders affecting taste and smell will be excluded, it is expected that these dysfunctions are present in 5% of the caregivers. If so, the differences between the patient and control group of caregivers can be assessed in a cohort of in total 49+49=98 patients and caregivers with a 95% confidence level and a power of 80%.

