8.1.2 Secondary study parameters/endpoints

- Salivary flow rate
- Salivary pH
- Salivary electrolytes and protein concentrations
- Perceived taste and smell dysfunction
- Perceived xerostomia (XI-scores and RODI-scores)

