Saliva flow will be measured, both stimulated and unstimulated(25). The pH of saliva will be determined immediately after collection using an electronic pH meter. The composition of the saliva is determined by measuring electrolyte concentration (Na, K, Cl, HCO₃, Zn) and the enzyme activity/concentrations of chitinase, amylase, lysozyme, Mucin5B, total protein, and carbonic anhydrase.

Questionnaires

Dysfunction in taste will be subjectively measured with the validated Dutch version of the CiTAS questionnaire(26). The CiTAS questionnaire consists of 18 questions on a 5-point Likert-scale and identifies the type and severity of taste dysfunction. The PG-SGA assesses weight, food intake, symptoms, and activities and function in 8 questions(27). The AHSP questionnaire consists of 29 multiple choice questions and assesses appetite, hunger and sensory perception(28). Impact on quality of life will be measured with the QOD questionnaire(29). Xerostomia will be quantified with the internationally validated XI (a questionnaire with 11 items on a 5-point Likert-scale) and the RODI(30,31). The RODI consists of a schematic representation of 9 intra-oral areas, and the patient can indicate the severity of the xerostomia at these areas on a 5-point Likert scale.

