10. STATISTICAL ANALYSIS

This study aims to investigate the prevalence of taste and smell dysfunction in a predefined cohort of melanoma, NSCLC and urogenital cancer patients. Results will be reported as mean (standard deviation) and median (range) for parametric and non-parametric continuous variables, respectively. Categorical data will be presented as N and percentages.

Participants and their caregivers will be compared using Mann Whitney U test or independent T-test, depending on data distribution. For ordinal data, Chi-square tests will be performed. Correlations between perceived and objective taste and smell dysfunction will be studied with Pearson's rho or Spearman's rho, depending on data distribution.

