10.2 Secondary study parameter(s)

Salivary flow rates, saliva electrolytes, salivary proteins, salivary enzyme activity and pH, perceived taste and smell dysfunction will be presented as mean scores and standard deviations.

Relationships between taste and smell dysfunction and salivary flow rates, salivar electrolytes, salivary proteins, salivary enzyme activity and pH will be analyzed using Pearson or Spearman correlation tests.

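### Section 10 sends ordinal data to chi-square tests, which ignore the order of 5-point severity ratings such as the RODI areas and lose power against a moderate shift

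*Combined protocol and SAP*

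**What the plan says.** Section 10 gives two rules for comparing the groups. The first is "Participants and their caregivers will be compared using Mann Whitney U test or independent T-test, depending on data distribution". The next sentence is "For ordinal data, Chi-square tests will be performed". No trend test, ordinal regression or other method that uses category order is named, and nothing later in the document overrides the rule.

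The ordered outcome concerned is the RODI. Section 8.2 describes nine intra-oral areas and says that "the patient can indicate the severity of the xerostomia at these areas on a 5-point Likert scale". Section 8.1.2 lists perceived xerostomia, measured by XI and RODI, as a secondary endpoint, and section 8.2 says that patients' results will be compared with those of caregivers. Section 10.2 says that "perceived taste and smell dysfunction will be presented as mean scores and standard deviations", but it mentions neither the XI nor the RODI. RODI ratings are therefore covered only by the general rules of section 10. The planned size, in section 4.4, is "49+49=98 patients and caregivers".

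**The concern.** A Pearson chi-square test gives the same result however the columns of the table are reordered. For a graded severity scale it discards the information the scale was built to collect and spreads its power over every possible pattern of difference.

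The mechanism proposed in section 1 is directional: gland damage, less saliva, a drier mouth. The alternative of interest is therefore a consistent shift towards more severe dryness, and a rank test is aimed at that kind of shift. As written, the plan names a rank test in one sentence and directs ordinal data away from it in the next. With about 49 per group, a moderate shift on a named secondary endpoint could be missed because of the choice of test alone.

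**Working it through.** **Step 1: the plan's own figure.** Section 4.4 assumes 25% against 5%, 80% power and 95% confidence. Sidedness is not stated; two-sided is inferred because it reproduces the plan's number. With pooled proportion 0.15 and no continuity correction:

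n = [1.96·√(2·0.15·0.85) + 0.842·√(0.25·0.75 + 0.05·0.95)]² / 0.20² = (0.9897 + 0.4080)² / 0.04 = 48.8, rounded up to 49 per group.

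Power at 49 is 80.1%. The figure reproduces. It concerns a binary outcome and is not affected by this point.

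**Step 2: the two tests on a 2×5 table.**
- Chi-square: X² = Σ(O−E)²/E over the ten cells, with (2−1)(5−1) = 4 degrees of freedom (fewer if a column is empty). Column order does not enter.
- Mann-Whitney with mid-ranks: z = [W − n₁(N+1)/2] / √V, where V = (n₁n₂/12)·[(N+1) − Σ(t³−t)/(N(N−1))] and t is the number tied at each level. It tests a single direction.

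**Step 3: the assumed alternative.** Control distributions and odds ratios (OR) are assumptions. The patient distribution is a proportional-odds shift: the odds of being at or below each level are the control odds divided by OR. For example, with an even control distribution the cumulative odds are 0.25, 0.667, 1.5 and 4. Dividing by 2.5 gives 0.10, 0.267, 0.60 and 1.60, so the patient proportions are 9.1, 12.0, 16.4, 24.0 and 38.5%.

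**Step 4: simulated power at 49 per group**, two-sided 0.05, 100,000 data sets per cell, shown as chi-square / Mann-Whitney (%):

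| Control distribution (%) | OR 1 | OR 1.5 | OR 2.0 | OR 2.5 | OR 3.0 | OR 4.0 |
|---|---|---|---|---|---|---|
| 20/20/20/20/20 | 5.0 / 5.0 | 12.0 / 20.2 | 28.8 / 48.3 | 48.8 / 71.2 | 66.0 / 85.2 | 86.3 / 96.4 |
| 50/25/15/7/3 | 4.0 / 5.0 | 10.4 / 19.0 | 26.2 / 45.7 | 46.0 / 69.3 | 63.8 / 84.4 | 85.8 / 96.3 |
| 70/15/8/5/2 | 3.5 / 5.0 | 8.5 / 16.4 | 21.6 / 39.7 | 39.1 / 62.6 | 56.3 / 79.3 | 81.0 / 94.4 |
| 10/20/40/20/10 | 4.7 / 5.0 | 11.0 / 19.4 | 26.9 / 46.5 | 46.6 / 70.1 | 63.6 / 84.5 | 85.5 / 96.3 |

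Subtracting within cells, the loss in percentage points is 7.9–8.6 at OR 1.5, 18.1–19.6 at 2.0, 22.4–23.5 at 2.5, 19.2–23.0 at 3.0 and 10.1–13.4 at 4.0. The OR 1 column is the type I error: chi-square is slightly conservative when the upper levels are sparse, and neither test is inflated.

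**Step 5: the loss in participants.** For 80% power at OR 2.5, in the row order above, chi-square needs 94, 98, 112 and 96 per group; Mann-Whitney needs 62, 64, 74 and 64. The ratios are 94/62 = 1.52, 98/64 = 1.53, 112/74 = 1.51 and 96/64 = 1.50.

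A separate simulation set OR so that the rank test has 80% power at 49 per group:

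| Control distribution (%) | OR | Chi-square power | Per group for chi-square to reach 80% |
|---|---|---|---|
| Even | 2.78 | 58.8% | 75 |
| 60/20/10/6/4 | 2.89 | 58.2% | 77 |
| 10/20/40/20/10 | 2.82 | 57.9% | 76 |

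**Step 6: where the loss shrinks or reverses.**
- Fewer levels: where the rank test has 80% power, chi-square has about 64% with four levels and 71% with three.
- Very large shift: section 4.4's 25% against 5% implies OR = (0.25/0.75)/(0.05/0.95) = 6.33. At that OR the loss is 1 point, though section 4.4's figures are for a binary outcome.
- Change in spread rather than level: for even against 35/10/10/10/35%, chi-square has 67% and the rank test 5–6%. For 10/20/40/20/10% against 30/15/10/15/30%, the figures are 97% and 6%.

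**The case against.** The strongest reply is that *ordinal* is a slip for *categorical*. Section 10 describes continuous data and then categorical data, and the tests follow in the same order. Read literally, the section names no test for binary or nominal data, although the study was sized on two proportions with the uncorrected formula that matches a chi-square test. This is plausible. It does not rescue the sentence, which as written still misdirects ordered ratings, and the same correction repairs both readings.

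Second, the RODI may be analysed as a score. Section 8.1.2 refers to scores, and the CiTAS, also built from 5-point items, contributes to outcomes presented as means. A summed RODI would fall under the Mann-Whitney or t-test rule, and the power loss would not arise for it. This stands as a limit: the figures apply only if areas are compared as ordinal ratings.

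Third, *chi-square tests* could include a test for trend, which uses order. Nothing in the text says so, and the unordered test is the usual reading.

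Fourth, the odds ratios and distributions are assumed, proportional odds favours the rank test, and the study was not powered for this endpoint. All true; hence the ranges and the contrary cases in the working. Caregivers are also recruited through patients, while the simulations treat the groups as independent, so the absolute powers are approximate for this design.

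**Conclusion.** The point holds. The written rule assigns ordinal data a test that ignores order, and it can reach a listed secondary endpoint. If RODI areas are compared as 5-point ratings and patients are shifted consistently towards greater dryness with an odds ratio of about 2 to 3, the cost is about 18 to 24 percentage points of power at 49 per group. Put another way, chi-square needs roughly half as many participants again. This assumes proportional odds, independent groups and the control distributions shown; the documents supply none of these for the RODI.

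The issue is power only. It does not touch the primary taste and smell scores, the perceived-dysfunction means, an XI total score, a summed RODI score or the sample size. It should be corrected because the remedy is cheap, but it does not threaten the main result.

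**What to change.** Replace the sentence in section 10 with:

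> Ordinal data (e.g. the RODI area ratings) will be compared between groups with the tie-corrected Mann-Whitney test (or a proportional-odds model). Chi-square or Fisher exact tests will be used for nominal and binary data only.

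One of the two ordinal methods should be named as the main one before the data are examined. Adding whether the RODI is analysed by area or as a summed score would make the rule's reach clear.

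The cost is one sentence. No data, visits or participants change, and the Mann-Whitney test is already in the plan. The price is less sensitivity to differences in spread that leave the average level unchanged.

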10.1 Primary study parameter(s)

Taste strip and Sniffin' Stick scores will be presented as mean scores and standard deviations. A higher score corresponds to a higher level of taste and/or smell dysfunction.

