2. OBJECTIVES

Primary Objective:

• To determine the prevalence of taste and smell dysfunction in patients more than two years after start of ICI therapy - compared with a control group of caregivers.

Secondary Objective(s):

- To assess the association between taste and smell dysfunction, and saliva secretion rate, saliva composition (pH, electrolyte and protein composition) and subjective feeling of a dry mouth (xerostomia) in patients more than two years after start of ICI therapy compared with a control group of caregivers.
- To assess the impact of taste and smell dysfunction in patients more than two years after start of ICI therapy.

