8. METHODS

8.1 Study parameters/endpoints

8.1.1 Main study parameter/endpoint

Taste and smell dysfunction measured using taste strips and Sniffin' Sticks in patients compared to caregivers.

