8.2 Study procedures

Both patients and caregivers are asked not to smoke, brush teeth, eat, or drink anything except water one hour before the tests. Then, unstimulated and chewing-stimulated saliva will be collected, the salivary flow rate will be measured using standardized procedures, and patients and caregivers will fill in two questionnaires regarding perceived taste and smell dysfunction. Taste and smell dysfunction will be assessed with taste strips and Sniffin' Sticks. To assess subjective taste and smell perception, and the impact of taste and smell dysfunction, the Chemotherapy-induced Taste Alteration Scale (CiTAS) questionnaire, the Patient-Generated Subjective Global Assessment (PG-SGA) questionnaire, the Appetite, Hunger and Sensory Perception (AHSP) and the Questionnaire of Olfactory Disorders (QOD) will be used. Subjective xerostomia will be assessed with the Dutch versions of the Xerostomia Inventory (XI) and the Regional Oral Dryness Inventory (RODI). The results of the patients will be compared with the caregivers. Salivary flow rate and pH will be measured immediately after collection, and subsequently the saliva will be stored at -80°C until biochemical analysis. Below, the tests and examinations are explained in more detail.

Taste dysfunction

Taste dysfunction will be objectively measured with "Taste Strips" (Burghart, Wedel, Germany)(23). Strips with an impregnated taste solution will be placed on the participants' tongue. The taste solutions contain the basic tastes bitter, sweet, sour and salty in four different concentrations, thus 16 tests will be performed. The strips will be randomly administered and participants are asked which taste they notice. A right answer gives one point and a total of 16 point can be obtained.

Smell dysfunction

Smell dysfunction will be objectively measured with "Sniffin' Sticks" (Burghart, Wedel, Germany)(24). Pens filled with liquid odorants are presented to the participants' nose. Participants will smell 16 different scents with an interval of minimal 30 seconds to

prevent desensitization. For each scent, participants will choose between four options from a multiple choice card. Smell threshold will be measured with "Sniffin' Sticks" with different odor concentrations.

Saliva (flow rate, pH and elektrolytes)

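### The objective and sample size rest on a prevalence of dysfunction (25% vs 5%), but the primary analysis is mean scores, and the yes/no event is never defined

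*Combined protocol and SAP*

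**What the plan says.** - **Objective (section 2):** "To determine the prevalence of taste and smell dysfunction in patients more than two years after start of ICI therapy", compared with caregivers. Section 10 opens with the same prevalence aim.
- **Sample size (section 4.4):** it expects that "long-term taste and smell dysfunction are prevalent in 25% of the patients" and, for controls, "it is expected that these dysfunctions are present in 5% of the caregivers". It concludes that the difference "can be assessed in a cohort of in total 49+49=98 patients and caregivers", at a 95% confidence level and 80% power. Neither the test nor its sidedness is named.
- **Endpoint (section 8.1.1):** "Taste and smell dysfunction measured using taste strips" and Sniffin' Sticks, patients against caregivers. No threshold for dysfunction is given.
- **Measurement (section 8.2):** for taste, "A right answer gives one point and a total of 16 point can be obtained". For smell, 16 scents are presented and "participants will choose between four options from a multiple choice card". A separate smell threshold test is also done. No scoring rule is given for either smell test.
- **Analysis (sections 10 and 10.1):** the primary scores "scores will be presented as mean scores and standard deviations", and section 10.1 adds that higher scores mean more dysfunction. Section 10 compares the groups by t-test or Mann-Whitney U test. It also provides for counts and percentages for categorical data, and chi-square tests for ordinal data, without linking either to the primary endpoint.

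**The concern.** The objective and the sample size ask what proportion of patients is affected and whether it exceeds the caregiver proportion. The analysis section written for the primary parameter answers a different question: by how much average scores differ. A mean difference does not determine a prevalence, so the primary quantity would not be produced.

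A prevalence cannot be calculated from this plan even by a willing analyst, because three choices are open: the cut-off on each test, the rule combining taste and smell, and whether smell identification or smell threshold counts. Left open, they could be settled after the data are seen, and the primary result depends on all three. The stated 80% power also describes a comparison that the analysis section does not commit to.

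Separately, section 8.2 awards a point per correct taste answer, so a high taste score is good performance, whereas section 10.1 treats a high score as dysfunction. Taken literally, the best tasters would count as the most impaired. No such conflict can be claimed for smell, where no scoring rule is stated.

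**Working it through.** **1. Reproduce the plan's figure.** Inputs from section 4.4: p1 = 0.25, p2 = 0.05, 95% confidence level (taken as two-sided alpha 0.05), power 0.80, equal groups. Mean proportion p̄ = 0.15. Pooled-variance formula without continuity correction:

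n = [1.960 × √(2p̄(1−p̄)) + 0.842 × √(p1(1−p1) + p2(1−p2))]² / (p1−p2)²

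= [1.960 × 0.5050 + 0.842 × 0.4848]² / 0.20² = (0.9897 + 0.4080)² / 0.04 = 48.84, rounded up to **49 per group**.

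Formula power at 49 is 80.1%. The plan's figure reproduces, which shows that the study was sized on a yes/no event.

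**2. Power depends on the unnamed test.** Full binomial enumeration at 49 per group, 25% vs 5%:

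| Test | Exact power |
|---|---|
| Chi-square, uncorrected | 84.7% |
| Fisher's exact | 73.5% |
| Chi-square, continuity-corrected | 73.5% |

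**3. Power depends on the unnamed cut-off.** Formula of step 1, patients held at 25%; the 10% and 15% caregiver rates are assumptions:

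| Caregivers labelled as cases | Power at 49 per group | n per group for 80% |
|---|---|---|
| 5% (section 4.4) | 80.1% | 49 |
| 10% | about 50% | 100 |
| 15% | about 23% | 250 |

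**4. What 49 per group means for scores.** A two-sided t-test (noncentral t, 96 degrees of freedom) has 80% power at a standardised difference of 0.572. The plan states no expected score difference or SD, so no intended power for this comparison can be derived from it.

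**5. A score difference does not fix a prevalence.** Assume normal scores with equal SD and patients shifted by 0.572 SD towards worse function. If the cut-off labels 5% of caregivers, patient prevalence is Φ(Φ⁻¹(0.05) + 0.572) = 14.2%. If it labels 10%, it is Φ(Φ⁻¹(0.10) + 0.572) = 23.9%. The same shift gives two quite different answers to the primary question.

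**6. What the objective would need (illustrative counts, close to the assumed rates).** 12/49 patients = 24.5%, Wilson 95% CI 14.6% to 38.1%. 2/49 caregivers = 4.1%, 1.1% to 13.7%. Difference 20.4 points, Newcombe 95% CI 6.6 to 34.3. The plan provides for no such intervals.

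**The case against.** The strongest reply is that section 10.1 only describes how scores are presented and does not exclude anything else. It sits under a section that opens with prevalence and allows counts and percentages, and the chi-square line for ordinal data may be loose wording for categorical data. On that reading prevalence was intended and only the link is implicit. The intention is plausible, but it does not supply the missing variable: without a cut-off and a case rule there is nothing to count or to enter into a chi-square test. Section 8.2 cites published sources for both tests, but citing a test does not adopt a cut-off from it.

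Second, the score comparison need not be underpowered. Under the normal, equal-SD assumption, 25% vs 5% implies a shift of Φ⁻¹(0.95) − Φ⁻¹(0.75) = 0.97 SD, for which a t-test at 49 per group has about 99.7% power. This stands, and no shortfall is claimed. The trouble is that the score test answers another question.

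Third, the direction sentence is probably a drafting slip, and reversing the scale changes neither the size of a score difference nor a two-sided p-value. That is fair for the score comparison. It would matter once a cut-off is applied, and the two sections do contradict each other for taste.

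Finally, scores are kept and can be dichotomised later, so no data are lost. True, but this is why the rule should be fixed before the data are analysed. Some controls are the patients' own caregivers; how the test handles those pairs is a separate refinement.

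**Conclusion.** The concern holds and must be fixed. As written, the plan does not deliver its primary quantity: the prevalence event is undefined, and no estimate or test of proportions is attached to it. The direction of the taste score in section 10.1 contradicts section 8.2.

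The sample size arithmetic is not in dispute. What is unsettled is what the 80% refers to. With the 25% and 5% rates, exact power at 49 per group is 84.7% or 73.5% depending on the test. If the chosen cut-off labelled 10% or 15% of caregivers, formula power would be about 50% or 23%. These figures treat the groups as independent, use two-sided 5% tests and, for the last two, assume caregiver rates that the plan does not state. The central conclusion needs no assumption; it follows from setting sections 2, 4.4, 8.1.1, 8.2, 10 and 10.1 side by side.

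**What to change.** Before any data are analysed:

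- **Sections 8.1.1 and 10.1:** specify one cited cut-off per test, one primary event (taste, smell, either or both) and the smell measure that enters it.
- **Section 10.1, scoring:** correct the direction sentence to agree with the taste scoring in section 8.2, and state the scoring rule for smell.
- **Section 10.1, analysis:** make the primary analysis the prevalence in each group with a 95% CI, and the difference in prevalence with a 95% CI and a named test of proportions. State how patient-caregiver pairs are handled. Keep the score comparison as supportive.
- **Section 4.4:** confirm that the 80% power refers to that single event with a two-sided uncorrected chi-square test, which is the reconstruction that fits 49 per group. Justify briefly that 25% and 5% apply to the chosen event, and restate the power if the event or test differs.

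The cost is text only: the tests are already planned, and no extra visits or enrolment are proposed. The downside is that the stated power may change once event and test are fixed, for example to 73.5% at 49 per group with Fisher's exact test.

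### Section 10.1 reads a higher taste-strip score as more dysfunction, but Section 8.2 scores right answers, so the stated direction of the taste half of the primary endpoint is reversed

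*Combined protocol and SAP*

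**What the plan says.** Section 8.1.1 makes taste and smell dysfunction, measured with taste strips and Sniffin' Sticks in patients and caregivers, the main endpoint.

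Section 8.2 describes the taste test as four basic tastes, each "in four different concentrations, thus 16 tests will be performed". The scoring rule follows: "A right answer gives one point and a total of 16 point can be obtained".

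Section 10.1 takes up the taste-strip and smell scores together. It says that the "Stick scores will be presented as mean scores and standard deviations", and then gives the only rule in the document for interpreting them: "A higher score corresponds to a higher level of taste and/or smell dysfunction".

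Three analyses use these scores:

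- Section 10, group comparison: "Participants and their caregivers will be compared using Mann Whitney U test or independent T-test, depending on data distribution".
- Section 10, agreement with self-report: "Correlations between perceived and objective taste and smell dysfunction will be studied with" Pearson or Spearman coefficients. One self-report instrument, the CiTAS, "identifies the type and severity of taste dysfunction" according to Section 8.2.
- Section 10.2, saliva: "Relationships between taste and smell dysfunction and salivary flow rates" and the other saliva measures, again by correlation.

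**The concern.** A score that adds a point for each correct answer rises with better taste. Section 10.1 says it rises with worse taste. Both sentences are intact, current text, and nothing else in the document converts one score into the other.

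What is at stake is the direction of the result. The sentence stands under the primary parameter, and no cut-off for dysfunction is given anywhere that would expose a wrong reading. An analyst who counts as 8.2 instructs and interprets as 10.1 instructs would describe a lower patient mean as less dysfunction than in caregivers. The correlations with perceived dysfunction and with saliva measures would be misread in the same way. A two-sided p-value is the same in either direction, so it would give no warning.

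**Working it through.** **Inputs**

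- Taste items: 4 tastes × 4 concentrations = 16 (Section 8.2).
- Points: 1 per correct answer, so the score X runs from 0 to 16 (Section 8.2).
- Stated direction: higher means more dysfunction (Section 10.1).
- Group size: 49 patients and 49 caregivers, based on prevalences of 25% and 5%, 95% confidence and 80% power (Section 4.4).
- Not in the document: the SD of the taste score and the sidedness of the tests. Two-sided 5% and an SD of 2 to 4 points are assumptions made here.

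**1. The plan's own figure.** With two independent proportions, pooled variance, a two-sided 5% level and no continuity correction:

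n = [1.96 × √(2 × 0.15 × 0.85) + 0.842 × √(0.25 × 0.75 + 0.05 × 0.95)]² / 0.20² = (0.990 + 0.408)² / 0.04 ≈ 48.8, rounded up to 49 per group.

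The stated 49 + 49 reproduces, with power 80.1%. It rests on prevalences, so the direction of the score does not affect it.

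**2. The two sections side by side**

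| Correct answers | Score under 8.2 | Reading under 10.1 | 16 minus correct |
|---|---|---|---|
| 16 | 16 | most dysfunction | 0 |
| 8 | 8 | middle | 8 |
| 0 | 0 | least dysfunction | 16 |

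The reading in 10.1 is right only for the last column, and the document does not define that score.

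**3. What a reversal changes.** Let Y = 16 − X. Then mean(Y) = 16 − mean(X) and SD(Y) = SD(X). A patient-minus-caregiver difference d becomes −d, and a correlation r becomes −r. The two-sided p-value and the absolute effect size stay the same. This step needs no assumption.

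**4. Illustration: results that could be misread.** The following figures describe a two-sample t-test with 49 per group, which is one of the two tests that Section 10 allows. They do not measure the wording error itself; they show how large a result might carry the wrong label.

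- Smallest significant observed difference: 1.985 × √(2/49) = 0.40 SD (df = 96).
- True difference detected with 80% power: 0.57 SD.
- In points out of 16, for an SD of 2 to 4: 0.8 to 1.6, and 1.1 to 2.3.
- Example: a 2-point patient deficit at SD 3 gives t = −2 / (3 × √(2/49)) = −3.30 on number correct and +3.30 on 16 minus correct. Both give p = 0.0014.

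**The case against.** The strongest reply is that this is a slip in one sentence. The scoring rule in 8.2 is explicit and its meaning is plain. For the result to be reported backwards, the team would have to count correct answers and then call more correct answers worse taste, and anyone familiar with the test would probably notice. That is fair: reversed reporting is possible but not shown to be likely, and the consequence should be stated as conditional.

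Three further points also stand. The t-test figures depend on assumptions that the plan does not fix: Section 10 also allows Mann-Whitney, no sidedness is stated, no SD is given, and Section 3 lets patients or caregivers take part alone, so equal groups are not assured. The sentence in 10.1 sets no cut-off, so by itself it does not alter a prevalence estimate. For Sniffin' Sticks nothing is contradicted: 8.2 describes 16 four-option items and a threshold test without a scoring rule, and cites a published method that may supply one.

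None of this reconciles 8.2 with 10.1 for taste strips. A pre-specified rule for the primary parameter should not rely on the analyst recognising that it is wrong.

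**Conclusion.** The concern holds. For taste strips, the direction given in Section 10.1 contradicts the scoring rule in Section 8.2, and the document defines no reversal that would reconcile them. This conclusion rests on the text alone.

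The size is a complete change of sign (d to −d, r to −r) if both sections are followed literally, and no change in anything else: two-sided p-values, absolute effects, sample size and raw data are untouched. The error can be corrected at any time before reporting. It should be corrected because it concerns the interpretation of the primary parameter. For smell, the direction is unverified and not shown to be wrong.

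**What to change.** Bring 10.1 into line with 8.2 for taste strips by one of two routes:

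1. Replace the direction sentence in 10.1 with: *A higher number of correct taste-strip answers corresponds to better taste function; a lower score indicates dysfunction.*
2. Keep the direction sentence and define the analysed taste score as 16 minus the number correct.

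The first is simpler, because it leaves the scoring in 8.2 as it stands. Whichever is chosen, apply the same direction to the group comparison and to the correlations in Sections 10 and 10.2.

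In the same edit it would help to add the Sniffin' Sticks scoring to 8.2 and to state the direction separately for identification and threshold. The 16-minus-correct rule should not be carried over to threshold, for which no 16-point scale is given.

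The cost is one sentence in 10.1 and, for smell, one or two in 8.2. Visits, participants and data are unaffected. Making the change before analysis avoids choosing a direction after the results are known.
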